We will test our central hypothesis in a randomized controlled trial (RCT) designed to determine if reduced insomnia symptoms result in improved CVD risk among those with co-morbid PTSD and Insomnia Disorder (ID). Specific and established CVD morbidity and mortality biomarkers of risk will be examined, including vascular endothelial function measured by brachial artery flow-mediated dilation (FMD), nighttime blood pressure (BP) dipping measured using 24-hour ambulatory blood pressure monitoring (ABPM), arterial stiffness measured by central pulse wave velocity (PWV), and atherosclerotic cardiovascular disease (ASCVD) risk score (Bonnet & Arand, 2007; Bonnet & Arand, 2010; Routledge & McFetridge-Durdle, 2007; Tsuji et al., 1996; Verdecchia, Angeli, Gentile, Mazzotta, & Reboldi, 2011). Insomnia will be measured *via* a multi-modal assessment strategy, including self-report and actigraphy. The *rationale* for the proposed research is if it is established that insomnia-related sleep impairment is a modifiable CVD risk factor among those with PTSD, new innovative approaches to integrating sleep treatment with PTSD focused interventions can be developed and implemented.

We will randomize 150 individuals with co-morbid PTSD and ID to either an 8-week CBT-I intervention or to a minimal contact control condition. Insomnia severity and objective sleep parameters, quality of life measures, and biomarkers of CVD risk will be assessed at baseline, post-intervention, and at a 6-month follow-up. Specific Aims include:

AIM 1: Determine whether CBT-I improves (a) CVD risk biomarkers, (b) 10-year ASCVD risk, and (c) quality of life (QoL) in persons with PTSD. *Hypothesis 1:* Compared to the control condition, CBT-I will be associated with increased sleep-efficiency and decreased insomnia severity (manipulation check), improved CVD risk biomarkers (Hypothesis 1a) including (i) lower nighttime BP and enhanced nighttime BP dipping, (ii) augmented vascular endothelial function (FMD), (iii) reduced sympathetic nervous system (SNS) activity (catecholamines), lower 10-year ASCVD risk score (Hypothesis 1b) and improved quality of life (Hypothesis 1c).

AIM 2: Determine whether within-person changes in sleep efficiency are accompanied by improved CVD risk biomarkers and 10-year ASCVD risk. *Hypothesis 2:* Within-person improvements in sleep efficiency (N=150) will be associated with improvements in CVD risk biomarkers and reduced ASCVD risk score.

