To examine whether increased sleep efficiency is associated with decreased CVD risk (Hypothesis 2), lagged values will be used to create changes scores, defined by subtracting values for sleep efficiency and each of the CVD risk parameters measured at time $t-1$ from those measured at time t . Thus, decreases will be reflected by negative change scores and increases by positive change scores. Linear MLM will then be used to model each of the change scores corresponding to the 6 aforementioned CVD risk variables using the general equation below:

$$\text{CVD risk}_{\Delta t} = B0 + B1 * \text{Sleep efficiency}_{\Delta t} + B2 * \text{CVD risk}_{t-1} + B3 * \text{Sleep efficiency}_{t-1}$$

where change in the CVD risk outcome from $t-1$ to t will be modeled as a function of corresponding change in sleep efficiency, covarying for sleep efficiency measured at $t-1$ and the outcome in question measured at $t-1$. To explore the heterogeneity of CBT-I treatment response on sleep (Supplemental Aim), potential moderators (trauma type, insomnia phenotype, medication use, biological sex, and minority status) of the effect of CBT-I treatment on sleep outcomes will be examined via interaction effects. Specifically, sleep efficiency and sleep quality measured at baseline, post-intervention, and 6-month follow-up will be modeled in separate analyses as a function of treatment, time, a given moderator, and their second- and third-order interactions. To avoid the effects of multicollinearity, each moderator will be tested in a separate analysis. To determine whether the effect of changes in sleep efficiency on changes in CVD risk parameters vary by each of the aforementioned moderators, the analyses specified above for Hypothesis 2 will be modified to examine the main effect of a given moderator as well as the interaction effect of the moderator and sleep efficiency on each of the CVD risk variables.

D.4. Sample Size and Power Considerations

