The second aim, which will examine within-person associations of changes in sleep efficiency with concomitant changes in cardiovascular indices, will have an ESS that is roughly equivalent to the total number of observations. With 150 participants contributing up to 2 change scores each, even with 10% attrition at each time point, the ESS is projected to be 256, which would have 80% power to detect an association equivalent to $\beta = .15$. A number of studies have established cross-sectional associations of sleep disturbance with cardiovascular risk factors (Spiegelhalder, Scholtes, & Riemann, 2010). In our own research, we have found that self-reported sleep disturbance is modestly associated with reduced heart-rate variability ($\beta = -.18$) and dyslipidemia (equivalent $\beta = .11$). We anticipate that these associations will be stronger in the proposed within-subjects analysis given the absence of random effects from between-person differences. Thus, the current trial should be sufficiently powered to detect even modest associations between concurrent changes in sleep efficiency and CVD risk parameters.

D.5. Data Sharing with Key Personnel Outside Duke

[name], at University of North Carolina at Chapel Hill, will perform some of the above-described statistical analyses in accordance with a sub-award to him. De-identified data will be shared with [name] via Box@Duke. No PHI, including dates, will be shared with [name].

E. STUDY TIMELINE

The overall data collection and analysis timeline is outlined in Table 3. Recruitment will occur in years 1 through 5. Intervention delivery and follow-ups will occur in years 1-5.

Table 3. Project Timeline

ACTIVITY	Year 1	Year 2	Year 3	Year 4	Year 5	Totals
Hiring/Training/Development	X					
Screening	26	48	47	47	31	199
Recruitment	20	35	35	35	25	150
DATA COLLECTION						
CVD & Sleep Measures	20	35	35	35	25	150
Treatment Waitlist	20	35	35	35	25	150
Post Assessment	15	38	34	32	23	142
6-month Assessment	0	40	38	41	23	142
Data Processing				X	X	
Data Analysis					X	

References

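### Aim 2 is stated as within-person, but the Hypothesis 2 equation adjusts for single lagged levels, so its sleep coefficient B1 also carries stable differences between people

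*Combined protocol and SAP*

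**What the plan says.** The Specific Aims set Aim 2 as: "Determine whether within-person changes in sleep efficiency are accompanied by improved CVD risk biomarkers and 10-year ASCVD risk". Hypothesis 2 repeats the term: "Within-person improvements in sleep efficiency (N=150) will be associated with improvements in CVD risk biomarkers and reduced ASCVD risk score". Section D.2 again describes Hypothesis 2 as concerning within-person associations. Section D.4 expects larger associations than in cross-sectional work "given the absence of random effects from between-person differences".

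Section D.3 gives the only model. Change scores are formed between successive visits, and "Linear MLM will then be used to model each of the change scores corresponding to the 6 aforementioned CVD risk variables". (The list in D.3 names five variables, not six.) The equation is

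ΔCVD(t) = B0 + B1·ΔSE(t) + B2·CVD(t−1) + B3·SE(t−1),

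where SE is sleep efficiency. In words, the outcome change "will be modeled as a function of corresponding change in sleep efficiency, covarying for sleep efficiency measured at" t−1 and for the outcome at t−1. The plan specifies no person-mean centring, person fixed effect, split into within and between parts, or random-effect structure.

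**The concern.** Regressing change on change removes whatever is constant in a person. Adding the lagged levels undoes part of that. If poor sleepers simply tend to have worse biomarkers, B1 can differ from zero although no one's biomarkers move with their own sleep. The error takes the sign of the between-person association. It favours Hypothesis 2 if better sleepers have lower risk, and can mask a real effect if the association runs the other way. It does not shrink as the sample grows. The stake is the interpretation of Aim 2: a significant B1 would be reported as a within-person finding when the model cannot separate the two sources.

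**Working it through.** **The plan's own figure.** D.4 states: "With 150 participants contributing up to 2 change scores each". It then assumes a 10% loss at both later visits and concludes that "the ESS is projected to be 256, which would have 80% power to detect an association equivalent to" a β of .15. First change score: 150 × 0.9 = 135. Second: 150 × 0.9² = 121.5. The sum is 256.5, so the 256 reproduces. The 80% power depends on unstated choices. A plain two-sided 5% test of .15 at n = 256 has about 67% power. It reaches 80% if the covariates explain 25% of the change-score variance. I use 256 change scores below.

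**Step 1: rearrange.** Moving CVD(t−1) to the right-hand side gives

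CVD(t) = B0 + B1·SE(t) + (1 + B2)·CVD(t−1) + (B3 − B1)·SE(t−1).

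So B1 is the partial slope of CVD(t) on SE(t), given one earlier reading of each variable.

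**Step 2: B1 with no within-person link.** Assume unit variances, a stable trait plus independent noise at each visit, the same ICC r for both variables, and cross-sectional correlation c arising only from the traits. Then SE(t) and SE(t−1) correlate at r, CVD(t) and CVD(t−1) correlate at r, and every sleep–CVD pair correlates at c. Solving the normal equations:

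B1 = c(1 − r) / (1 + r − 2c²).

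This is zero only if c = 0 or r = 1.

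**Step 3: inputs.** All are assumptions for Aim 2.
- r = .50 is given in D.4 for Hypothesis 1; range .3 to .7.
- r = .81 is the repeat-FMD correlation in C.6.2 (healthy volunteers, consecutive days), so an upper guide.
- Absolute c = .18 and .11 come from D.4: self-reported sleep disturbance against heart-rate variability and dyslipidemia. At r = .5 they imply between-person correlations of .18/.5 = .36 and .11/.5 = .22, which the documents do not state.

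**Step 4: results.** With equal ICCs the partial correlation equals B1. Rejection is Φ(t − 1.96) + Φ(−t − 1.96), with t = √[256·B1²/(1 − B1²)]. For r = .5 and c = .18: B1 = .09/1.4352 = .063, t ≈ 1.0, rejection 17.1%.

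| ICC r | c (absolute) | B1 (absolute) | Rejection, formula | Rejection, simulated |
|---|---|---|---|---|
| .3 | .18 | .126/1.2352 = .102 | 37.5% | 36–37% |
| .5 | .11 | .055/1.4758 = .037 | 9.2% | 7–11% |
| .5 | .18 | .090/1.4352 = .063 | 17.1% | 16–18% |
| .7 | .18 | .054/1.6352 = .033 | 8.3% | 7–9% |
| .81 | .18 | .0342/1.7452 = .020 | 6.1% | 6–7% |

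The simulations used 150 people and three visits with 10% then 10% dropout, or 256 change scores directly. Under this data model, a person-mean-centred or person fixed-effects analysis rejected about 4–7%. At 1,000 change scores, the r = .5, c = .18 case rejects about 51%.

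**Step 5: do other features of the plan remove it?**
- *Random intercept:* rejection changes by no more than 0.1 point. A compound-symmetry error structure that allows negative correlation lowers 18.4% to 13.4%, without curing it.
- *CBT-I effect on sleep efficiency:* at r = .5 and between-person correlation .36, rejection is about 16–17% with d = 0.54 and 12% with d = 1.48.
- *FDR correction (D.1):* at r = .5, c = .18, a given outcome is declared in 7.4% of null trials (five outcomes), but at least one outcome in 28–29% (five or six). The at-least-one figure is 13–15% at c = .11, and 10–12% at r = .7, c = .18.

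**Step 6: a real within-person slope.** With slope .15, ICC .5 and no between-person correlation, the planned equation averages .123 with 51% power. The fixed-effects model averages .148 with 67%.

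**The case against.** Adjusting for lagged levels is a recognised model. It is the right one if biomarkers carry over from visit to visit, or if earlier CVD state affects later sleep, and the documents rule out neither. The trait-plus-noise model above is a choice. Under carry-over the centred model has its own costs. With assumed carry-over of .5 and a true slope of −.18, power was about 81% for the planned equation and 70% for the centred one. With no sleep effect but feedback of −.18 from earlier CVD state to sleep, false positives were about 6–7% for the planned equation and 10% for the centred one. The inputs are also borrowed: heart-rate variability and dyslipidemia are not among the biomarkers listed in D.3, and self-report is not actigraphy.

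All of this stands, and it limits the claim. A reader might infer that Aim 2 will be falsely positive, that the lagged equation is simply invalid, or that a centred model costs nothing. The documents support none of these. They give no ICC or between-person association for the Aim 2 variables, and the distortion is slight if the ICC is high. What the objection does not answer is the mismatch in wording: the plan does not argue for carry-over. It claims a within-person analysis from which between-person differences are absent, and its equation lacks that property.

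**Conclusion.** The point holds as a mismatch between the stated aim and the specified model. It follows from the algebra wherever a stable between-person association exists and the lagged readings are imperfect measures of it. Its size rests on the assumptions in Steps 2 and 3. At ICC .5 and the borrowed correlations, spurious B1 is about .04 to .06 against a design target of .15, with per-outcome rejection of about 8–18% before FDR. At a correlation of .18 the rate runs from about 36–38% (ICC .3) through 8–9% (ICC .7) to 6–7% (ICC .81). Aim 2 can therefore be declared positive with no within-person link; it does not follow that it will be. The plan should be corrected before analysis, but this is not a fatal flaw: Aim 2 is an observational association, and the randomised comparison in Aim 1 is unaffected.

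**What to change.** For each outcome, fit a mixed model on levels at all three visits: visit, sleep efficiency minus the person's own mean, the person's mean sleep efficiency, and a random intercept. Rest the within-person claim of Hypothesis 2 on the centred term. Add treatment and treatment-by-visit terms, at least as a sensitivity analysis, because a CBT-I effect on CVD risk that does not act through sleep would otherwise load on the centred term.

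Keep the lagged-level equation as a labelled sensitivity analysis for carry-over, and declare a within-person link only where the centred term supports it. Do not fall back on change-on-change with the lags simply dropped. That version had 71–74% power against about 80% in the case with no stable confounding, and about 17% false positives under feedback.

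The cost is SAP wording and one extra model per outcome, with no new data. Some power is lost (about 70% against 81% in the assumed scenario) if biomarkers carry over and there is no stable confounding. One gain is that people who miss only the post-intervention visit still contribute; the t−1 rule gives them no change score.

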Supplemental Aim: Explore the heterogeneity of CBT-I treatment response on sleep and CVD risk. We will explore moderators of improvements in sleep and CVD risk biomarkers following CBT-I including primary trauma type, insomnia disorder phenotype (objectively measured short sleep duration vs. objective normal sleep duration), medication use, biological sex, and minority status.

With respect to *expected outcomes*, the proposed work should establish whether unconsolidated sleep contributes to mechanisms conveying CVD risk burden in persons with PTSD. Identification of modifiable determinants of the relationship between PTSD and CVD risk is expected to have an important *positive impact* on the medical management of PTSD.

A. RESEARCH STRATEGY: SIGNIFICANCE AND INNOVATION

Several studies have now linked PTSD to increased cardiovascular disease (CVD) morbidity and

mortality (Boscarino, 2006; Edmondson et al., 2013; Flood et al., 2010), including a two-fold increase in the risk of premature death from CVD (Boscarino, 2008). While the distinct mechanisms underlying this association remain unclear, evidence suggests that PTSD contributes to CVD morbidity and mortality independent of health risk behaviors (e.g., smoking) and comorbid depression (Boscarino, 2008; Vaccarino et al., 2013). A recent review of the available evidence described PTSD as “a fast-track to premature cardiovascular disease” concluding that there was a lack of mechanistic evidence regarding the progression of atherosclerosis in PTSD, and a need to examine CVD risk biomarkers (Wentworth et al., 2013). Establishing the mechanism(s) linking PTSD to CVD is an essential next step in identifying therapeutic targets to reduce cardiovascular risk in this vulnerable population (Committee on Veterans’ Affairs House of Representatives Subject, 2010).

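### No model in D.3 combines treatment, a moderator and a CVD outcome, so the planned CVD moderator analysis does not estimate the heterogeneity of CBT-I response that the Supplemental Aim promises

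*Combined protocol and SAP*

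**What the plan says.** The Supplemental Aim in the Specific Aims reads: "Explore the heterogeneity of CBT-I treatment response on sleep and CVD risk". It continues: "We will explore moderators of improvements in sleep and CVD risk biomarkers following CBT-I", and names five moderators: trauma type, insomnia phenotype, medication use, sex and minority status. Both outcome domains are framed as response to CBT-I.

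D.3 (Primary and Secondary Analyses) restates the aim more narrowly: "To explore the heterogeneity of CBT-I treatment response on sleep (Supplemental Aim"). Potential moderators "of the effect of CBT-I treatment on sleep outcomes will be examined via interaction effects". The outcomes are given explicitly: "sleep efficiency and sleep quality measured at baseline, post-intervention, and 6-month follow-up will be modeled in separate analyses", on treatment, time, one moderator and their interactions.

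For CVD outcomes the stated purpose is "To determine whether the effect of changes in sleep efficiency on changes in CVD risk parameters vary by each of the aforementioned moderators". The method is to modify the Hypothesis 2 model by adding the moderator's main effect and "the interaction effect of the moderator and sleep efficiency on each of the CVD risk variables". The Hypothesis 2 model is the one "where change in the CVD risk outcome from $t-1$ to t will be modeled as a function of corresponding change in sleep efficiency", adjusting for the lagged values of both. Treatment is not among its terms.

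**The concern.** The aim asks whether CBT-I changes CVD risk more in some kinds of patient than in others. That is a treatment by moderator contrast on a CVD outcome, and it can use the randomised comparison. The planned CVD analysis instead relates two post-randomisation changes, pools the arms, and asks whether the strength of that relation varies by subgroup.

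A subgroup can gain more CVD benefit because its sleep improves more at the same slope, or through a route other than sleep. It can also have a steeper slope and no greater benefit. If the slope interaction stands in for CVD response to CBT-I, real heterogeneity may be missed and apparent heterogeneity suggested where there is none. What is at stake is the interpretation of an exploratory aim.

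**Working it through.** **1. Which terms appear together in which model**

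| Model | Outcome | Treatment | Moderator |
|---|---|---|---|
| D.3, Hypothesis 1a | CVD variables | yes | no |
| D.3, Hypothesis 2 | CVD change | no | no |
| D.3, Supplemental Aim, part 1 | sleep efficiency, sleep quality | yes | yes |
| D.3, Supplemental Aim, part 2 | CVD change | no | yes (by sleep-efficiency change) |

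No row has a CVD outcome with yes in both columns. D.1 mentions stratifying by trauma exposure and sleep duration, but this is in the descriptive paragraph, covers two of the five moderators and states no treatment by moderator test.

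**2. Do the two quantities agree?** The effects here are assumed and standardised, because the documents give none. Take one interval, 2:1 allocation and a binary moderator at 50%. Let a be the effect of CBT-I on sleep change, b the slope of CVD change on sleep change, and c any effect of CBT-I on CVD outside sleep. The total effect on CVD in a subgroup is a × b + c. A simulation with n = 2,000,000, without the lagged covariates, gave the values in the last two columns.

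| Case | Subgroup 0 | Subgroup 1 | True difference in CVD effect | Treatment × moderator | Planned slope × moderator |
|---|---|---|---|---|---|
| A: same slope, unequal sleep gain | a 0.2, b 0.3, c 0 | a 0.8, b 0.3, c 0 | 0.24 − 0.06 = 0.18 | 0.18 | 0.00 |
| B: unequal slope, same total effect | a 0.8, b 0.2, c 0 | a 0.4, b 0.4, c 0 | 0.16 − 0.16 = 0 | 0.00 | 0.20 |
| C: only a non-sleep route differs | a 0.5, b 0.3, c 0 | a 0.5, b 0.3, c 0.4 | 0.40 | 0.40 | 0.04 |

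In case C the small planned term is leakage from the omitted treatment effect. With unit residual variance it is 0.4 × [0.5 × 2/9] / [0.25 × 2/9 + 1] = 0.4 × 0.111 / 1.056 = 0.04.

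**3. Precision of the missing analysis.** The documents give no power figure for this aim, so I start from the Aim 1 figure in D.4.

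- Effective sample size = N × m / [1 + (m − 1) × ICC] = 150 × 3 / (1 + 2 × 0.5) = 225, as stated.
- With 10% lost at each step, 121.5 people have three visits, 13.5 have two and 15 have one. This gives 121.5 × 1.5 + 13.5 × 1.333 + 15 × 1 = 215.25, against the stated 215.
- At 2:1 (143.3 and 71.7), detectable d = (1.960 + 0.842) × √(1/143.3 + 1/71.7) = 2.802 × 0.1447 = 0.405, against the stated 0.41. The plan's figure reproduces.

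For a treatment by moderator interaction with moderator prevalence p (assumed, since none is given), SE = √[(1/143.3 + 1/71.7) × (1/p + 1/(1 − p))].

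| p | SE | Detectable d at 80% power | Power at d = 0.41 |
|---|---|---|---|
| 50% | 0.289 | 0.81 | 29% |
| 30% | 0.316 | 0.88 | 25% |
| 20% | 0.362 | 1.01 | 20% |

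**4. Number of added models.** Five moderators × the five CVD variables that D.3 lists = 25. D.3 speaks of six variables but names five; a sixth would make 30. With two planned time contrasts each, 25 models give 50 contrasts. If these were tested at 0.05 and all were null, 50 × 0.05 = 2.5 false positives would be expected.

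**The case against.** The strongest reply is that D.3 is coherent in itself. It attaches treatment response to sleep only, and it states the purpose of the CVD moderator model accurately as a question about slopes. D.2 reasons in the same way: its missing-data argument for Hypothesis 2 and this aim rests on the sleep-CVD association. Studying CVD through sleep also fits the central hypothesis. On this view the fault lies in the wording of the aim, and rewording would cure it. That stands as an alternative remedy, but as written the aim and the analysis still name different quantities.

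Three stronger readings are tempting, and the documents do not support them.

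- **Who gains cardiovascular benefit cannot be answered.** This is true only of the models as specified. Treatment, moderators and CVD outcomes are all collected. The planned sleep interaction may also pick up some of the heterogeneity. Assume 150 people at 2:1, two equal subgroups, sleep gains of 1.5 and 0.5 SD and a common slope of 0.4. The sleep interaction then has SE √[(1/100 + 1/50) × 4] = 0.346 and power of about 82%. The CVD interaction is 0.4 with SE 0.346 × √1.16 = 0.373 and power of about 19%. Going from the sleep result to CVD benefit, however, needs mediation assumptions and a non-randomised slope, and the plan does not combine the two pieces. It also misses non-sleep routes, as in case C.
- **The planned CVD interaction is zero by construction.** That holds under a common slope with all of the effect passing through sleep, not in general.
- **A null slope interaction will be reported as no heterogeneity of CVD response.** Nothing in the documents says so.

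The cost also counts against the added models: they are numerous, uncorrected and imprecise.

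**Conclusion.** The mismatch is real and can be read directly from the text. The planned CVD moderator term can be null when the CVD effect of CBT-I differs by subgroup, and non-null when it does not. The sizes in cases A to C illustrate this and rest on assumed effects; they do not predict this trial's results.

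The consequence is limited. The aim is supplemental and exploratory, D.1 exempts it from alpha correction and says that supported findings would need validation, and D.4 bases power on Aims 1 and 2 only. No primary conclusion depends on it. The point is still worth correcting, because a stated analysis targets a different quantity from the aim it serves and the data needed are already being collected. The detectable interaction of about d = 0.8 is a best case, resting on the protocol's own effective sample size of 215 and an even moderator split.

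**What to change.** In D.3, extend the treatment by time by moderator sentence so that it covers each Hypothesis 1a CVD variable as well as sleep efficiency and sleep quality. Label these models exploratory and report subgroup effects with confidence intervals rather than significance tests. Add one sentence saying that the moderator by sleep-change models address the sleep-CVD association and not CVD response to CBT-I.

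The cost is a few lines of text and about 25 further uncorrected models with wide intervals. They will seldom identify who benefits and should be presented accordingly. No new data are needed.

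If the sponsor prefers not to add them, narrow the Supplemental Aim in the Specific Aims to match D.3 (CBT-I response on sleep, plus variation in the sleep-CVD association), and make no claim about which patients gain cardiovascular benefit from CBT-I.
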